Pediatric experience: Fanale et al (2011) conducted a retrospective analysis of two phase 1 and two phase 2, multicenter brentuximab vedotin drug development studies which included the enrollment of pediatric patients age 12-17 years old. Nine patients (median age=16 years, male=5) were included in this analysis. Patients received brentuximab vedotin, as a 30 minute outpatient infusion, at dose of either 0.8 mg/kg or 1.2 mg/kg weekly for 3 out of 4 weeks or doses of 1.2 mg/kg or 1.8 mg/kg every 3 weeks (median of 15 cycles). The majority (n=6) of patients received 1.8 mg/kg every 3 weeks. Complete response was observed in 6/9 pediatric patients who had treatment-refractory lymphoma. Grade ≥ 3 treatment-emergent adverse events included neutropenia (n=3), white blood cell count decreased (n=1), thrombocytopenia (n=1), catheter site infection (n=1) and hyperesthesia (n=1). No patient discontinued treatment due to an adverse event.

1.4 Rationale for New Cohort :

With 30 evaluable patients to date, data from the phase II portion of this study show an ORR of 75% and a CR rate of 33.3%. Among patients who achieved CR after 2 cycles of treatment, all remained in CR after 2 additional cycles of treatment and were able to proceed to AHCT without further intervening therapy. For patients who only achieved PR or SD after 2 cycles of therapy, 2 additional cycles of brentuximab vedotin, given at the 1.8mg/kg dose, did not change the response rate in any patient, either from PR to CR or SD to PR. Ultimately all patients, with the exception of one went on to AHCT after additional therapy. Although it is medically acceptable and allowed as part of the COH standard operating procedure to take a patient with PR to AHCT, retrospective data from Memorial Sloan Kettering show better PFS when patients enter AHCT with CR as disease status (Moskowitz et al.). For that reason, the majority of our patients in PR or SD received combination chemotherapy such as ICE (ifosfamide, Cyclophosphamide, Etoposide) to convert from PR to CR or SD to PR/CR before AHCT.

Because data from the phase II portion of this study showed that the observed conversion

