2.2 Secondary Objectives

The secondary objectives of this study are:

- To characterize the safety, toxicity and tolerability of brentuximab vedotin as a salvage regimen.
- To summarize the stem cell mobilization results of patients receiving brentuximab vedotin as salvage therapy (e.g., total CD34+ cell yield, number of apheresis days, proportion of patients who achieve $\geq 3 \times 10^6$ CD34+ cells/kg)
- To evaluate potential changes in Hodgkin lymphoma biological markers of patients treated with brentuximab vedotin as 1st line salvage therapy.
- To examine and characterize the outcomes of patients who receive brentuximab vedotin as 1st line salvage followed by AHCT (e.g., 2-year PFS/OS/relapse-progression incidence and NRM).

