3 INVESTIGATIONAL PLAN

This is an open label, phase II study of brentuximab vedotin in patients with Hodgkin lymphoma prior to autologous hematopoietic stem cell transplantation (AHCT). Patients must have either primary refractory disease (failed to achieve complete remission after ABVD chemotherapy) or have relapsed after ABVD. Patients cannot have had another line of treatment after ABVD. Patients may have had BEACOPP as upfront induction chemotherapy instead of ABVD. Patients also can have consolidative radiotherapy in conjunction with ABVD. Patients will start treatment with brentuximab vedotin as salvage therapy prior to AHCT. Brentuximab vedotin will be given at dose of 1.8 mg/kg on D1 every 21 days for a total of 4 cycles.

The primary efficacy endpoint of this study is response rate. This is a phase II efficacy trial. Response will be assessed according to modified criteria for malignant lymphoma, based on (Cheson *et al.* 1999) and (Cheson, *et al.* 2007). Response assessment will be performed after every two cycles.

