7.4 Pharmacodynamic/Pharmacogenomic/Correlative Studies

A paraffin block from the representative diagnostic section or 12 unstained paraffin slides will be obtained from diagnostic materials and also at the time of relapse (if available). We will analyze for CD 30 and CD 68 expression. We will confirm CD 30 expression prior to enrollment in trial. Patients must have CD 30 expression in original diagnostic material or relapsed material. We will examine the CD 68 expression in the original and relapsed material and attempt to correlate with response. For patients who have biopsy material available at relapse or progression, we will collect DNA/RNA from the tumor specimen and perform microarray analysis and compare with before and after treatment.

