In accordance with the primary study objectives, we will perform descriptive statistical analyses on these data after the study is complete. With adequate follow-up time, the endpoints of PFS, overall survival (OS) will be assessed by Kaplan-Meier survival analysis and 95% confidence intervals will be calculated using Greenwood's formula. PFS will be defined as the time from first treatment day (post AHCT) until objective or symptomatic relapse or death as a result of lymphoma or acute toxicity of treatment. OS will be defined as the time from first treatment day (post AHCT) until death. The cumulative incidence of relapse/progression and non-relapse mortality will be calculated as competing risks.

8.2 New Cohort to Test Increased Dosing for Patients Not Achieving CR after Two Cycles

Based on previously published brentuximab vedotin response/toxicity data and data from the phase II portion of this study (see protocol section 1.3), we now propose to accrue up to 20 additional patients in a new cohort that will enroll until we have 10 patients who do not attain CR after two cycles of therapy, and are treated at the increased dose of 2.4 mg/kg of brentuximab vedotin for cycles 3 and 4. The goal of this study is to evaluate the impact of treating non-CR patients (after two cycles of therapy) at an increased dose (from 1.8 mg/kg to 2.4 mg/kg) during cycles 3 and 4. We believe that the 2.4 mg/kg dose will be well tolerated (defined as $\leq 33\%$ of patients with \geq grade 3 non-hematologic toxicity that is assigned an attribution level of at least possibly related to the study drug during cycle 3 or 4) and that treating these patients at the increased dose will increase the CR rate.

With a CR rate of 33.3% -after two cycles of therapy, we expect to achieve 10 patients without CR (in the first 2 cycles) after 15 patients are enrolled (maximum enrollment 20, which has $>90\%$ chance of having 10 patients without CR in first two cycles). With 10 patients treated at the escalated dose of 2.4 mg/kg, with a conversion rate of 25%, the probability of not getting at least one response is less than 6%. If the first 2 cycle response data are pending, accrual will not hold. Accrual will only hold based on stopping due to toxicity, or when 10 patients are treated at the escalated dose of 2.4mg/kg. Patients who are treated with at least one cycle at 2.4 mg/kg will be evaluable at that dose level, even if later dose reduced or discontinued.

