8.5 Statistical methods

The toxicities observed will be summarized in terms of type (e.g. organ affected or ANC) severity (by NCI CTCAE 4.0 and nadir or maximum values for the laboratory measures), date of onset, duration, reversibility, and attribution. Table will be created to summarize these toxicities and side effects. Baseline information (e.g., the extent of prior therapy) and demographic information will be presented for all patients.

In accordance with the primary study objectives, we will perform descriptive statistical analyses on the data after the study is complete. Response will be assessed by Cheson 2007 criteria and reported as percentage of the evaluable study population. With adequate follow-up time, the secondary endpoints of PFS, overall survival (OS) will be assessed by Kaplan-Meier survival analysis and 95% confidence intervals will be calculated using Greenwood's formula.

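### The only PFS definition names relapse but not progression, so 2-year PFS can be overstated for patients transplanted without CR and can disagree with the relapse/progression incidence

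*Combined protocol and SAP*

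**What the plan says.** The secondary objectives (Section 2.2) give as example outcomes "2-year PFS/OS/relapse-progression incidence and NRM". PFS is defined once, in the analysis text of Section 8.1. The clock starts on the first treatment day, with post AHCT in brackets, and runs "until objective or symptomatic relapse or death as a result of lymphoma or acute toxicity of treatment". The disease event is relapse, and the deaths that count are limited by cause. Two sentences later, the same paragraph says: "The cumulative incidence of relapse/progression and non-relapse mortality will be calculated as competing risks". Section 8.5 repeats that "the secondary endpoints of PFS, overall survival (OS) will be assessed by Kaplan-Meier survival analysis", with no definition of its own.

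Patients can reach transplant without CR. Section 1.4 says it is "medically acceptable and allowed as part of the COH standard operating procedure to take a patient with PR to AHCT". It adds that most patients in PR or SD had further chemotherapy first, and it does not report how many were still short of CR at transplant.

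**The concern.** PFS and the relapse/progression incidence are two views of the same post-transplant course, yet their disease events are worded differently. A patient who enters transplant in PR and whose disease then grows has progressed; having never been in CR, the patient has not relapsed in the strict sense. The protocol draws this distinction elsewhere. Section 3 describes eligible patients as having "primary refractory disease (failed to achieve complete remission after ABVD chemotherapy) or have relapsed after ABVD", and Section 7.4 writes "For patients who have biopsy material available at relapse or progression".

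The stake is the credibility of a reported 2-year PFS. The error can run only upward. It would fall on patients transplanted without CR, the group that Section 1.4 expects to have worse PFS. Two analysts working from the same data could also report different PFS curves, depending on how each read one word.

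**Working it through.** **No figure to reproduce.** The protocol states no expected 2-year PFS, event count or power for PFS. The check is to apply the written rule to cases and then bound its effect.

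**Step 1: apply the rule literally.** The times are illustrative.

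| Patient | PFS under the Section 8.1 wording | Relapse/progression incidence |
|---|---|---|
| A: CR at AHCT, relapse at month 8 | event at 8 | event at 8 |
| B: PR at AHCT, never in CR, progression at month 5, alive at month 24 | no event by 24 | event at 5 |
| C: as B, but dies of lymphoma at month 20 | event at 20 | event at 5 |

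B is missing from 2-year PFS. C is delayed by 15 months, but is still an event by 2 years.

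**Step 2: consistency.** With a common origin and complete event lists,

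PFS(t) = 1 − relapse/progression incidence(t) − NRM(t).

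Under the written rule this fails in two places. Patients like B are in the incidence curve but not in PFS. Deaths without relapse or progression that are not due to acute toxicity are in NRM but not in PFS. Both gaps push the sum of the three above 100%.

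**Step 3: size of the progression gap.** Let
- f = share transplanted without CR (assumed; not in the documents)
- q = 2-year progression risk in that group (assumed)
- s = share of those progressors dead of lymphoma by 2 years, who therefore still count (assumed)

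Ignoring censoring, the overstatement of 2-year PFS is f × q × (1 − s).

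At f = 0.20, in percentage points:

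| q | s = 0 | s = 0.25 | s = 0.50 |
|---|---|---|---|
| 0.2 | 4.0 | 3.0 | 2.0 |
| 0.4 | 8.0 | 6.0 | 4.0 |
| 0.6 | 12.0 | 9.0 | 6.0 |

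The corners are 0.20 × 0.2 × 0.5 = 0.02 and 0.20 × 0.6 × 1 = 0.12.

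At q = 0.4 and s = 0.25, varying f:

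| f | 0 | 0.10 | 0.20 | 0.33 | 0.667 |
|---|---|---|---|---|---|
| points | 0 | 3.0 | 6.0 | 9.9 | 20.0 |

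The last column is an extreme bound. It takes the interim CR rate of 33.3% in Section 1.4 and supposes that no other patient reached CR with further salvage (1 − 0.333 = 0.667).

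**Step 4: in patients.** If all 37 are transplanted, each uncounted progressor adds 100/37 = 2.7 points. The 2 to 12 point range is then 0.02 × 37 = 0.7 to 0.12 × 37 = 4.4 patients.

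A patient who reaches CR after transplant and later relapses is counted correctly. Taking f as everyone not in CR at transplant therefore leans toward the high side.

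**The case against.** The strongest reply is that relapse is shorthand here and any sensible analyst would count progression. There is real support for that. The endpoint is called progression-free survival. The term non-relapse mortality, paired with relapse/progression, only works if relapse covers both. Section 7.1 records PD, SD, PR or CR and has no separate relapse category, so regrowth after PR and return after CR would both be recorded as PD. Section 3 describes status at entry rather than events after transplant, and Section 7.4 also uses the word loosely.

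This makes the intended meaning plausible and the overstatement conditional. It does not remove the problem, because the analyst would have to override the only written rule, in a paragraph that names both events for the companion endpoint.

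Three stronger readings are tempting but not supported:

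- *That progressors without CR are never PFS events and 2-year PFS is overstated.* Lymphoma death counts, so some events are only delayed. Any overstatement at 2 years needs patients transplanted without CR who progress, and literal use of the word.
- *That the size can be derived by taking the 88% 1-year OS in Table 1 as survival after progression.* That figure is overall survival in a separate study of 102 patients treated after a prior autologous transplant. It is not stated to run from progression.
- *That adding progression alone makes the three outcomes sum to 100%.* It does not while other-cause deaths stay outside PFS.

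**Conclusion.** The definition is incomplete and, applied as written, delays or misses progression in patients never in CR. The bias on PFS can only be upward, and PFS can disagree with the relapse/progression incidence defined in the same paragraph.

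The documents do not fix the size. It is zero if all patients are transplanted in CR, and about 2 to 12 points at 2 years if 20% are not. That range rests wholly on the assumed 20% share, a progression risk of 20-60%, and 0-50% of progressors dead of lymphoma by 2 years.

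PFS is a descriptive secondary endpoint with no hypothesis or decision rule. The primary response-rate test and the sample size are untouched, and progressions would still appear in the separate incidence analysis. The wording should be corrected, but it does not threaten the trial's main conclusion.

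**What to change.** In Section 8.1, make two edits together:

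1. Define the PFS disease event as *objective or symptomatic relapse or progression, dated at first documentation*. State that the cumulative incidence of relapse/progression uses the same disease-event list and the same time origin.
2. Widen the deaths in PFS from those due to lymphoma or acute toxicity to *death from any cause*.

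The analyst can then check that PFS, relapse/progression incidence and NRM sum to 100% at 2 years. The first edit without the second would not pass that check.

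The cost is a change of wording. No new data are needed, because progressions and non-relapse deaths must already be recorded for the competing-risks analysis. The reported PFS may be slightly less favourable.

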11.1.2 Monitoring and Personnel Responsible for Monitoring

The Protocol Management Team (PMT) consisting of the PI, Collaborating Investigator, CRA/protocol nurse, and statistician is

responsible for monitoring the data and safety of this study, including implementation of the stopping rules for safety and efficacy.

Data and safety will be reported to the COH DSMC using the PMT report and submitted quarterly from the anniversary date of activation. Protocol specific data collection will include the following items: hematological response, and toxicities of treatment. Reporting of data and safety to the DSMB will occur at the time of planned endpoints or unanticipated problems and at least once per year using the PMT report. The planned endpoint is overall response rate as determined by radiographic imaging after 2nd and 4th cycle of treatment. We will perform interim analysis after 17 patients have accrued on study and report to the DSMB and also after 37 patients have accrued on study.

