11.3 Reporting of Unanticipated Problems and Adverse Events

Unanticipated Problems: Most unanticipated problems must be reported to the COH DSMC and IRB **within 5 calendar days** according to definitions and guidelines at <http://www.coh.org/hrpp/Pages/hrpp-policies.aspx>. Any unanticipated problem that occurs during the study conduct will be reported to the DSMC and IRB by submitting electronically in iRIS (<http://iris.coh.org/>).

Serious Adverse Events - All SAEs occurring during this study, whether observed by the physician, nurse, or reported by the patient, will be reported according to definitions and guidelines at <http://www.coh.org/hrpp/Pages/hrpp-policies.aspx> and Table 2 below. Those SAEs that require expedited reporting will be submitted electronically in iRIS (<http://iris.coh.org/>).

Adverse Events - Adverse events will be monitored by the PMT. Adverse events that do not meet the criteria of serious OR are not unanticipated problems will be reported only in the continuation reports and PMT reports (see Table 2 below).

Table 2: City of Hope Adverse Event and Unanticipated Problem Reporting Timelines for the DSMC and IRB

Required Reporting Timelines to DSMC for AE/SAEs
Investigator Initiated Studies

Required Reporting Timeframe to DSMC		
Attribution	UNEXPECTED	EXPECTED
	Death while on active treatment or within 30 days of last day of treatment	
Possibly, Probably, Definitely	5 calendar days	
Unlikely, Unrelated	Death after 30 days of last active treatment/therapy	
Possibly, Probably, Definitely	5 calendar days	No reporting required
Unlikely, Unrelated	No reporting required	No reporting required
	Grades 3 and 4 AND meeting the definition of "serious"	
Possibly, Probably, Definitely	5 calendar days	10 calendar days
Unlikely, Unrelated	5 calendar days	10 calendar days
	Grades 1 and 2 AND resulting in "hospitalization"	
Possibly, Probably, Definitely	5 calendar days	10 calendar days
Unlikely, Unrelated	10 calendar days	10 calendar days

Externally Sponsored Studies

Required Reporting Timeframe to DSMC		
Attribution	UNEXPECTED ¹	EXPECTED
	Death while on active treatment or within 30 days of last day of treatment	
Possibly, Probably, Definitely	No DSMC reporting required - IRB reporting may be necessary	
Unlikely, Unrelated	Death after 30 days of last active treatment/therapy	
Possibly, Probably, Definitely	No DSMC reporting required - IRB reporting may be necessary	

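### Section 8.2 relies on a toxicity stop for the 2.4 mg/kg cohort, but the supplied text states no rule and attaches no action to the 33% tolerability limit

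*Combined protocol and SAP*

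**What the plan says.** Section 8.2 enrols up to 20 patients until 10 without CR after two cycles have been treated at 2.4 mg/kg in cycles 3 and 4. On the plan's figures, "we expect to achieve 10 patients without CR (in the first 2 cycles) after 15 patients are enrolled". Accrual does not pause while cycle 2 responses are pending. The grounds for a hold are: "Accrual will only hold based on stopping due to toxicity, or when 10 patients are treated at the escalated dose of 2.4mg/kg".

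The one toxicity figure is introduced as an expectation: "We believe that the 2.4 mg/kg dose will be well tolerated (defined as" at most 33% of patients with a grade 3 or higher non-hematologic toxicity, at least possibly related, in cycle 3 or 4.

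Section 11.1.2 makes the Protocol Management Team (PMT) responsible for monitoring, "including implementation of the stopping rules for safety and efficacy", without naming this cohort. Its named analyses are an "interim analysis after 17 patients have accrued on study and report to the DSMB and also after 37 patients have accrued on study". On routine reporting it says: "Data and safety will be reported to the COH DSMC using the PMT report and submitted quarterly from the anniversary date of activation". The DSMB receives reports "at the time of planned endpoints or unanticipated problems and at least once per year".

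Section 11.3 says "Adverse events will be monitored by the PMT". Its Table 2 sends serious grade 3-4 events to the DSMC within 5 calendar days if unexpected and 10 if expected, whatever the attribution. Section 11.6 has participating sites report SAEs within 24 hours. Section 5.5 modifies doses patient by patient, and 12.8 permits early closure.

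**The concern.** The plan leans on a stop that cannot be carried out as written. The efficacy rule is explicit in 8.1 (12 responders of 23, then 23 of 37). No safety counterpart appears: no boundary, no look, no consequence. The interim analyses at 17 and 37 patients fit the original 37-patient study, and none is named for the escalated patients.

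The stake is patient safety above the MTD. Section 1.4 reports dose-limiting toxicity in 3 of 12 patients at 2.7 mg/kg and 1 of 12 at 1.8 mg/kg. If a fourth escalated patient has a qualifying event, more than 33% of the planned 10 are affected, yet nothing written requires a hold before the next escalation. A discretionary stop also has no operating characteristics for the DSMC or IRB to judge.

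**Working it through.** **Figures stated in 8.2.** These reproduce:
- Expected enrolment: 10 / (2/3) = 15.
- P(Bin(20, 2/3) ≥ 10) = 0.962, above the stated 90%.
- 0.75^10 = 0.056, below the stated 6%.

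No corresponding figure is given for toxicity.

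**What the limit means.** 3/10 = 30% meets it and 4/10 = 40% does not, so a fourth event is the natural trigger for a cohort of 10.

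**What a fourth-event hold would do.** Let p be the true rate of qualifying events. The best case is that each patient's outcome is known before the next is escalated.
- Chance of a hold before the tenth escalation = P(Bin(9, p) ≥ 4).
- At p = 0.25: 1 − (0.0751 + 0.2253 + 0.3003 + 0.2336) = 0.166.
- Mean number escalated = Σ P(Bin(n−1, p) ≤ 3) over n = 1 to 10.
- Patients spared = 10 minus that mean.

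The delayed column drops the best-case assumption. Its inputs are:
- 8.1's expected accrual of 37 patients in 3 years, arriving at random;
- 2/3 of them non-CR, so a mean of 44.4 days between escalations;
- assumed event times, uniform over the 42 days of cycles 3 and 4.

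| True rate p | P(limit met in 10) | Hold before 10th, best case | Mean escalated | Spared | Hold before 10th, delayed outcomes |
|---|---|---|---|---|---|
| 20% | 0.88 | 9% | 9.80 | 0.2 | 7% |
| 25% | 0.78 | 17% | 9.59 | 0.4 | 14% |
| 33% | 0.57 | 34% | 9.09 | 0.9 | 30% |
| 40% | 0.38 | 52% | 8.50 | 1.5 | 46% |
| 50% | 0.17 | 75% | 7.52 | 2.5 | 69% |

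The 25% row is nearest to a rate in the documents (3/12 at 2.7 mg/kg). It is an imperfect proxy, because the dose and the event definition both differ. If the count were acted on only at quarterly reports, the delayed chance would fall from 30% to 22% at p = 33%, and from 69% to 56% at p = 50%.

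**Which existing provisions could act as the rule.**
- Section 5.5 acts on one patient's dose, not on the cohort.
- Table 2 and 11.6 bring serious events quickly to the DSMC and the principal investigator, but require no hold.
- A related grade 3 or higher event that is not serious has no expedited DSMC route. It goes into continuation and PMT reports unless it is an unanticipated problem.
- DSMC action to suspend or amend in 11.3 follows an unanticipated problem, which must be unexpected in nature, severity or frequency.
- Section 12.8 leaves closure to judgement.

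**The case against.** The strongest reply is that oversight is already fast. With a mean of 44.4 days between escalations, the chance that nobody new is escalated within 10 days is exp(−10/44.4) = 80%, and within 5 days it is 89%. The DSMC would therefore usually have a serious event before the next escalation. This stands, and it rules out reading the plan as leaving the cohort unmonitored. Receiving a report is still not a required hold, and the route omits non-serious events that count toward the 33%.

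Second, 11.1.2 speaks of safety stopping rules in general. A reader might infer that it promises a rule for this cohort. It does not; only 8.2 makes that link.

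Third, the rule may exist elsewhere. The Section 14 appendices and the institutional monitoring plan cited in 11.1.1 were not supplied. No appendix title in the contents list names a stopping rule, but the institutional plan cannot be checked. The finding is limited to the supplied text.

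Fourth, 33% defines tolerability and is not offered as a boundary. That is correct, and turning it into a trigger is a proposal. Nor does a fourth event always put the limit out of reach. Non-CR patients already enrolled when the tenth is escalated might also be escalated. On the accrual assumptions above, the number exceeds 10 in about 59% of cohorts that reach 10, and is 13 or more in about 6%, where 4/13 = 31% would still meet the limit.

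Fifth, the benefit is small, exposure is two cycles, and 1.4 reports safe use of 2.4 mg/kg in another institutional study and no dose reductions among 37 patients. All of this bears on urgency. None of it supplies the missing rule.

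**Conclusion.** The point holds: 8.2 depends on a toxicity stop that the supplied text does not define, and the 33% figure leads to no action. Existing safeguards make a cohort-level stop possible but leave it to discretion. This should be corrected because the dose is above the MTD and the remedy is short, not because many patients would be spared. The saving is under 1 of 10 at true rates up to 33% and about 2.5 at 50%, in the best case of immediate outcomes and exactly 10 planned escalations.

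A reader might infer that 2.4 mg/kg is unsafe. The documents do not show that: 1.4 argues for the dose, and the 3/12 rate comes from 2.7 mg/kg.

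**What to change.** In 8.2, state that:
- accrual and new escalations to 2.4 mg/kg are held for DSMC review as soon as the PMT knows that a fourth escalated patient has a related grade 3 or higher non-hematologic toxicity in cycle 3 or 4, without waiting for a scheduled report;
- non-CR patients who reach cycle 3 during a hold continue at 1.8 mg/kg;
- escalation is capped at 10 patients or, if pending non-CR patients may also be escalated, the fourth event still triggers review;
- the best-case hold probabilities are as tabulated, labelled as best case.

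In 11.1.2, add the running count of these events, serious or not, to each PMT report. If a rule already exists in another document, cite it in 8.2.

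The drafting cost is a few sentences. The operating cost is a best-case hold in 9% of cohorts at a true 20% and 17% at 25%. An assumed hold of 4 to 6 weeks would catch about 28/44.4 = 0.63 to 42/44.4 = 0.95 non-CR patients. They would stay on 1.8 mg/kg, for which 1.4 reports no improvement in response after cycle 2. If the hold is lifted and they do not count toward the 10, each needs about 1.5 further enrolments on average. Within the cap of 20, the chance of reaching 10 escalated falls from 96% to 91% with one held, P(Bin(20, 2/3) ≥ 11), or to 81% with two, P(Bin(20, 2/3) ≥ 12).
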